## METHODS OVERVIEW

We will voluntarily enroll 70 inpatients admitted to the University of Chicago Medicine over the course of 12 months into the at-home BREATHES Program. After obtaining informed consent, participants will complete in-hospital skills, lung function, and medication adherence assessments followed by the BREATHES at-home V-TTG inhaler learning program with self-monitoring and adherence support through the SpiroPD device. Participants will be trained on V-TTG and SpiroPD use in the hospital. The V-TTG intervention uses novel adaptive learning features that allow learners to participate in tailored educational sessions. They will begin every-other-day lung function assessments using the SpiroPD device in the hospital and continue on discharge. At 48-72 hours after discharge, participants will receive a unique username and password to complete the at-home V-TTG sessions on any of their own desktop or handheld devices; they will complete the V-TTG session at least one time in the first 30 days. Participants will receive reminders for completion of the V-TTG inhaler training and daily lung function monitoring via text messaging Adherence to the at-home V-TTG session (captured through the Smart Sparrow platform), lung function monitoring (captured via the SpiroPD device), and objective inhaler medication adherence (captured via Propeller Health Bluetooth objective monitoring; only 30 of these 70 patients will have objective medication adherence captured) will be assessed throughout the 30-days after discharge via the HIPAA compliant interface. Participants will return at 30 days post-hospital discharge for an in-person evaluation of their inhaler skills, lung function, and acute care utilization.

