## Study Schema

Table 1: Data Collection Tools		Hospital	Home	30-day
V-TTG adherence	Smart Sparrow platform data capture	-	X	-
Inhaler technique	Validated inhaler checklists	X	-	X
Inhaler knowledge, efficacy, skills	Inhaler step knowledge , applied inhaler use skill , and attitudes for inhaler self-efficacy assessed through short-answers.	X	X	X
Lung function	KoKo® portable spirometer: lung function (FEV1 %predicted). Handheld SpiroPD device (up to daily, at home)	X X	- X	X X
Treatment Adherence	Self-reported: Medication adherence report scale (MARS); dose-counter on applicable devices; optional medication diary on the SpiroPD device Objective: Propeller Health® Bluetooth devices.	X -	- X	X X
Self-efficacy	"I am confident that I know how to use [inhaler] correctly, (5-point scale).	X	X	X
Quality of life (QOL)	The Airway Questionnaire (AQ-20) 20-item tool assesses effect of current symptoms in everyday life for patients with COPD.	X	-	X
Symptoms	Modified Borg Dyspnea Scale; COPD Severity Score.	X	-	X
Health Literacy	Short Test of Functional Health Literacy in Adults: 36 item tool.	X	-	X

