## **Data Collection Time Points**

1. *In-Hospital Baseline Assessments*. Research Assistant (RA) will assess participants' baseline inhaler technique, inhaler self-efficacy, lung function, and self-reported adherence to their treatment regimen.

2. *In-Hospital Education*: Research Assistant (RA) provides in-person TTG inhaler training and training on how to use the V-TTG and lung function monitoring at home.

3. *In-Hospital Post-Education Assessments*. RA will obtain post-education assessments.

4. *Post-Discharge At-Home BREATHEs Program with V-TTG education and lung function monitoring*. The participant will complete up to daily lung function (goal of every other day) and medication adherence diaries using the SpiroPD device. The RA will give a unique username and password to each participant to access the V-TTG inhaler training after they have been discharged home. The V-TTG should be completed at least once within the first 30 days after discharge. The RA will send up to three reminders for completion of the lung function monitoring and V-TTG via text messaging. Participants will use their own device (tablet, laptop or desktop computer, or smartphone) for V-TTG use at home. For some patients, data will be collected each time they use their inhaled medication as prescribed. This data will be collected automatically when medication is utilized via a Propeller Health device attached to the inhaler. Patients should use their medication as they are instructed by their provider; no specified usage will be provided by the research team. Only data from regular use will be collected for this portion of the study.

5. *Post-Discharge Assessments*. Thirty days (+/-7 days) after discharge, participants will return for an in-person study visit to assess inhaler technique, adherence measures, lung function, and other assessments.

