## **STATISTICAL ANALYSES**

We will use means, medians, proportions, scatterplots, and histograms to describe the data. We will test for group differences using the *t*-test, the Wilcoxon rank sum test, Pearson's chi-squared test, or Fisher's exact tests, as appropriate. The primary outcomes for Aim 1 are at-home V-TTG adherence and inhaler technique and for Aim 2, at-home lung function testing adherence and medication adherence. McNemar's chi-squared tests will be used to compare 30 day post-discharge vs. pre-discharge adherence to the devices, prevalence of inhaler misuse ( $\leq 10/12$  steps correct), and medication adherence. Secondary outcomes will include change in

self-efficacy for inhalers, symptom burden, self-reported utilization of health care services, and QOL. A two-tailed p-value less than 0.05 will define statistical significance.

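### Aim 2's primary medication-adherence test names no instrument, analysis set or cut-off; a paired analysis of the MARS change would define it with data already collected

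*Combined protocol and SAP*

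**What the plan says.** STATISTICAL ANALYSES gives the primary outcomes "for Aim 2, at-home lung function testing adherence and medication adherence". It then states: "McNemar's chi-squared tests will be used to compare 30 day post-discharge vs. pre-discharge adherence to the devices, prevalence of inhaler misuse", with a definition of misuse (10 or fewer of 12 steps), and ends the list with "steps correct), and medication adherence". Misuse therefore has a cut-off; medication adherence has none.

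The candidate measures appear elsewhere:

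- **Table 1, self-reported.** MARS, then "dose-counter on applicable devices; optional medication diary on the SpiroPD device". The row is marked for the hospital and the 30-day visit.
- **Table 1, objective.** "Objective: Propeller Health® Bluetooth devices", marked for home and 30 days, with a dash for the hospital.
- **Data Collection Time Points, step 1.** The baseline assessment covers "inhaler self-efficacy, lung function, and self-reported adherence to their treatment regimen".
- **Data Collection Time Points, step 4 (post-discharge).** "This data will be collected automatically when medication is utilized via a Propeller Health device attached to the inhaler". The same step has participants completing medication diaries on the SpiroPD, with no mention that this is optional.
- **METHODS OVERVIEW.** "only 30 of these 70 patients will have objective medication adherence captured) will be assessed throughout the 30-days after discharge".
- **Survey Data Collection.** MARS is the only adherence instrument listed, at enrollment and at 30 days.
- **TYPE AND NUMBER OF EXPERIMENTAL SUBJECTS.** The Propeller subset is chosen by inhaler compatibility and willingness.

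**The concern.** McNemar's test needs a yes/no status for each patient at both times. For medication adherence the plan supplies neither the variable nor the rule that makes it yes or no. Someone must choose an instrument, a set of patients and a cut before the test can be run. If that choice is made after the data are seen, the stated two-sided 5% level is no longer assured.

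This matters because PURPOSE & HYPOTHESIS predicts that SpiroPD use will significantly improve medication adherence, so the result will be read as a test and not only as description. There is also a cost in information: splitting a score into two categories usually discards part of the change that the study collects at both visits.

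**Working it through.** **1. Which measure can form a pre/post pair?**

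| Measure | Pre-discharge | 30 days | Coverage |
|---|---|---|---|
| MARS | yes | yes | all participants |
| Dose counter | Table 1 row marked | Table 1 row marked | applicable devices only |
| SpiroPD diary | Table 1 row marked | Table 1 row marked | optional in Table 1; expected in step 4 |
| Propeller | none scheduled | post-discharge | about 30 of 70, selected |

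The Propeller row does not depend on reading a broken table: METHODS OVERVIEW and step 4 both place it after discharge, and step 1 lists only self-report at baseline. Used in the planned test, Propeller would give 0 scheduled pairs. MARS gives up to 70, but only once a cut is set.

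**2. What would the binary analysis cost?** The plan states no power, SD, correlation, shift or MARS cut, so there is no figure of its own to reproduce. What follows is illustration under assumed inputs: bivariate normal scores, n = 70 (from the plan), two-sided 0.05 (from the plan), within-patient correlation ρ = 0.3 to 0.7, and shift δ in baseline SD units.

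*Paired t.* The non-centrality is δ√n / √(2(1−ρ)). At δ = 0.35 and ρ = 0.5 it is 0.35 × 8.367 / 1 = 2.93, which gives 82% power.

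*McNemar at a median cut, same inputs.* Under the model 24.1% move from below to above the cut and 10.4% move the other way. The difference is d = 0.137 and the discordant share is ψ = 0.344. Power ≈ Φ[(d√n − 1.96√ψ)/√(ψ − d²)] = Φ[(1.145 − 1.150)/0.571] ≈ 50%. Simulation gives 52% for the uncorrected test and 42% for the exact test.

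Simulated power over ρ = 0.3 to 0.7:

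| Assumed shift (SD) | Paired t | McNemar, median cut, uncorrected |
|---|---|---|
| 0.2 | 29-56% | 18-26% |
| 0.35 | 68-96% | 44-62% |
| 0.5 | 94-100% | 73-89% |

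**3. Where the ranking changes.** With 40% of baseline scores at the ceiling and a shift of 0.35 SD, the figures for ρ = 0.3/0.5/0.7 are 53/65/83% for the paired t and 44/52/62% for McNemar, so the gap narrows. If a gain of 0.70 SD occurs only in patients who would otherwise be below the cut, McNemar is ahead: 95/98/99% against 77/88/97%.

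**4. Does the cut matter by itself?** The share of simulated trials in which a 20th-percentile cut and a median cut give opposite significance verdicts on the same patients (uncorrected test) is about:

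- 0.2 SD: 22-30%
- 0.35 SD: 36-47%
- 0.5 SD: 36-40%
- 0.7 SD: 13-26%

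Over shifts of 0.2 to 0.7 SD this is about 13-47%. With no shift it is about 9%.

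**The case against.** The strongest reply is that MARS is plainly meant: baseline adherence is self-reported, MARS is the only adherence instrument in the survey list, and Table 1 separates self-report from objective capture. That reading is probably right, and it disposes of one stronger inference. A reader might conclude that the plan commits to an impossible test on Propeller data. It does not: STATISTICAL ANALYSES never says that Propeller enters the McNemar comparison. But accepting MARS still leaves the cut and the analysis set unstated.

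A second reply is that McNemar on a pre-specified binary is legitimate, and that preferring a t-test is a matter of taste. The first half stands, and one scenario above favours McNemar. Still, no binary is specified, and a paired analysis of the score needs no cut at all.

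Third, a reader might infer that two reasonable cuts will usually disagree. The documents give no shift to support that. The disagreement rate depends strongly on the assumed shift, and it partly reflects two tests of moderate power as well as the missing cut.

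Finally, patients diagnosed during the hospitalization are eligible, and some may have no earlier regimen to report. This is possible, but the documents give no number, and it is not why the analysis set is undefined. The set is undefined because none is stated.

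**Conclusion.** The point holds in this form: medication adherence is an Aim 2 primary outcome with a named test but no instrument, analysis set or cut-off. MARS can supply the pre/post comparison; Propeller cannot. The documentary part rests on no assumption.

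The size is illustrative. At an assumed shift of 0.35 SD, analysing the MARS change instead of a median split raises power from about 44-62% to about 68-96%. The advantage is smaller with a ceiling effect and reversed if gains are confined to patients below the cut. Normality, shift, correlation and cuts are all assumed.

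Separately, Table 1 and step 4 of Data Collection Time Points disagree on whether the SpiroPD medication diary is optional, and should be reconciled. The plan should be changed before analysis, but the defect is readily repaired.

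**What to change.** In STATISTICAL ANALYSES:

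1. Define the Aim 2 medication-adherence analysis as the 30-day minus baseline MARS score in all participants with both assessments, with one paired test chosen now (paired t or Wilcoxon signed-rank) and a 95% CI.
2. Keep McNemar on dichotomised MARS as secondary, with its cut-off and version (uncorrected or exact) fixed before data are seen.
3. Report Propeller separately as a post-discharge estimate with a CI, labelled as a selected subset with no baseline.
4. Reconcile Table 1 with step 4 on the diary, and say what role, if any, the diary and dose counter have in this outcome.

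**Cost.** Wording only for the MARS analysis, since MARS is already collected at both visits. Expressing Propeller as a percentage of prescribed doses would also need the prescribed regimen, which Table 1 and Survey Data Collection do not list; without it, report recorded use.

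**Downside.** The pre/post measure is self-report, and a mean score change is less directly interpretable than a proportion adherent. A single-arm change also cannot exclude regression to the mean or reporting bias.

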## **Device Data Collection**

The SpiroPD device will record participant use and lung function scores. These measurements are stored in a HIPAA compliant server over wifi and are available to the participant and research team. Data from the V-TTG educational modules will be collected via the Smart Sparrow platform. For a subset of approximately 30 patients, a device by Propeller Health will measure objective medication use and adherence. This device will collect only use of an inhaler medication and does not require the participant to use their treatment any differently than prescribed by the clinician. This data will be stored in a HIPPA compliant server only available to the research team.

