## **Spirometry**

Spirometry will be performed during the initial visit and during the follow up visit using the portable KoKo spirometer and the SpiroPD device.

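### The pre/post McNemar test of device adherence has no valid pre-discharge counterpart; for SpiroPD it can report a decline when behaviour has not changed

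*Combined protocol and SAP*

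**What the plan says.** STATISTICAL ANALYSES names the primary outcomes: "The primary outcomes for Aim 1 are at-home V-TTG adherence and inhaler technique" and, "for Aim 2, at-home lung function testing adherence and medication adherence". One sentence then applies McNemar's chi-squared test, 30 days after discharge against before discharge, to three items: "to compare 30 day post-discharge vs. pre-discharge adherence to the devices", inhaler misuse, and medication adherence. Only misuse has a stated cut-off (at most 10 of 12 steps correct). The word devices is not defined.

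The timing of each measure is given elsewhere:

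- **V-TTG.** "At 48-72 hours after discharge, participants will receive a unique username and password to complete the at-home V-TTG sessions" (METHODS OVERVIEW). Table 1 marks V-TTG adherence as not collected in hospital. Under the heading Device Data Collection the protocol adds: "Data from the V-TTG educational modules will be collected via the Smart Sparrow platform".
- **Propeller.** Used in 30 of the 70 participants. Table 1 marks it as not collected in hospital, and METHODS OVERVIEW places its assessment in the 30 days after discharge.
- **SpiroPD.** "They will begin every-other-day lung function assessments using the SpiroPD device in the hospital and continue on discharge" (METHODS OVERVIEW). Also, "Spirometry will be performed during the initial visit and during the follow up visit using the portable KoKo spirometer and the SpiroPD device" (Spirometry). Data Collection Time Points, item 4, sets a goal of every other day and allows up to daily use.
- **Medication adherence.** Table 1 lists MARS, dose counters, an optional SpiroPD diary and Propeller. MARS is the only adherence instrument listed under Survey Data Collection, at enrolment and at 30 days.

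**The concern.** McNemar's test needs the same yes/no measure on the same person at both times. It also assumes that the measure means the same thing each time, so that only behaviour can move it.

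At-home use of a device cannot be observed before the participant goes home. Where no in-hospital value exists, the test cannot be run. Where an in-hospital value does exist, as for SpiroPD, it comes from a short supervised stay of unstated length, and the chance of being classed adherent depends on how many tests were scheduled. Two primary outcomes are exposed in this way: at-home lung function testing adherence, and at-home V-TTG adherence if V-TTG counts as a device. A third, medication adherence, has no measure or cut-off tied to its test, so both could be chosen after the data are seen.

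**Working it through.** **1. Is there a pair?** Setting the test sentence beside Table 1 and the data-collection sections:

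| Item | Value before discharge | Value after discharge | Cut-off stated |
|---|---|---|---|
| At-home V-TTG (if a device) | None | Yes | At least one session in 30 days |
| Propeller (if included) | None | Yes | None |
| SpiroPD | Inpatient tests, number unstated | About 15 tests | Goal only |
| MARS | Yes | Yes | None |
| Inhaler misuse | Two: baseline and post-education | Yes | At most 10 of 12 |

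The first two rows give no paired table. Coding everyone non-adherent before discharge would not rescue the test. One discordant cell would be zero by construction, and six adherent participants would then be enough for significance: exact p = 2 × 0.5^6 = 0.031. Six is 6/70 = 8.6% of the sample, or 6/30 = 20% of the Propeller subset.

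**2. SpiroPD: what would the test show if nobody changed?** The plan gives no power or discordance figure to reproduce, so this is an illustration. From the documents: n = 70, two-sided 0.05, and every other day for 30 days = 15 home tests. Assumed: 1-6 inpatient tests (stays of 1-12 days at one test per two days), and a personal completion probability that follows a Beta distribution with mean m = 60, 70 or 80% and SD 0.25, identical in both periods.

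The Beta parameters satisfy a + b = m(1−m)/0.25² − 1, with a = m(a + b). For m = 0.7: 0.21/0.0625 − 1 = 2.36, and a = 1.652. The chance of completing all k scheduled tests is the product of (a+i)/(a+b+i) for i = 0 to k−1. For k = 3: (1.652 × 2.652 × 3.652)/(2.36 × 3.36 × 4.36) = 0.46.

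| Scheduled tests | m = 60% | m = 70% | m = 80% |
|---|---|---|---|
| 1 | 60% | 70% | 80% |
| 2 | 42% | 55% | 70% |
| 3 | 32% | 46% | 64% |
| 6 | 19% | 32% | 54% |
| 15 (home) | 8% | 18% | 41% |

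If the initial-visit test always counts as done, k inpatient tests behave like k−1, and a single test gives 100%. The fall from the upper rows to the last comes only from the number of tests.

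From 4,000 simulated trials per setting, using exact McNemar, with ranges over m (and over the 50% and 80% cuts in the third row):

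| Meaning of adherent | Initial test counted | Initial test not counted |
|---|---|---|
| Full goal: false decline | about 75-100% | about 55-100% |
| Full goal: false increase | essentially none | essentially none |
| 50% or 80% of tests: false decline, with 1/2/3/4/5/6 inpatient tests | 97-100/51-100/3-55/0-96/6-82/10-76% | 0-97/3-53/0-1/0-26/0-34/2-17% |
| 50% or 80% of tests: largest false increase | about 8% | about 32% |

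The lowest full-goal figures occur with six inpatient tests. A valid test would give a false result in either direction in at most 5% of trials.

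**3. Medication adherence on MARS.** With an assumed shift of 0.35 SD, correlation 0.5 and n = 70, the signed-rank test on the score has 81% power. McNemar has 40-53% (uncorrected) or 31-43% (exact), depending on the cut. With an assumed ceiling (43% at the maximum score at baseline), the figures are 65% against 34-53% and 26-43%. Over nine shift and correlation scenarios, the gain over the best uncorrected cut is 8-33 points without the ceiling and 3-21 with it.

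**4. Precision of estimates instead.** The SD of a person's percentage over 15 tests is √[0.0625 + (m(1−m) − 0.0625)/15]: 0.273 at m = 0.6 and 0.263 at m = 0.8. The 95% half-width at n = 70 is 1.995 × SD/√70, or 6.3 to 6.5 points. Exact 95% intervals for observed proportions of 50%, 70% and 90% are 37.8-62.2%, 57.9-80.4% and 80.5-95.9% at n = 70, and 31.3-68.7%, 50.6-85.3% and 73.5-97.9% at n = 30.

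**The case against.** The strongest reply is that the test was never meant for V-TTG or Propeller. The protocol calls V-TTG an intervention or a learning program, used on the participant's own equipment, and the statistical section does not name Propeller. MARS is the obvious paired measure of medication adherence. This largely stands. A reader might infer that the plan orders impossible tests on all 70 participants for V-TTG and on the whole Propeller subset; the documents support that only if those undefined terms include them. The narrower reading still leaves V-TTG adherence, a primary outcome, with only the general statement "We will use means, medians, proportions, scatterplots, and histograms to describe the data" and no denominator or interval.

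The SA1 hypothesis mentions in-hospital V-TTG, which might suggest a baseline. Data Collection Time Points, item 2, instead describes in-person TTG plus training in how to use V-TTG. Table 1 schedules no in-hospital V-TTG adherence measure, and a supervised session would not measure at-home adherence.

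A reader might also infer that the SpiroPD test always leans towards decline. It does so under the full every-other-day goal in this model. At 50% or 80% cuts the direction varies, and the plan fixes no cut. Stay length and adherence rates are assumptions.

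Finally, an adherent/non-adherent proportion is a legitimate endpoint. The signed-rank test is not required for MARS: with a ceiling its advantage may be only a few points, and McNemar with a cut-off fixed in advance is also acceptable.

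**Conclusion.** The concern holds for device adherence. The absence of an in-hospital value for V-TTG and Propeller follows from the documents alone; whether the McNemar sentence reaches them depends on how devices and medication adherence are read. For SpiroPD, which that sentence does reach on any ordinary reading, the test can be computed but does not measure change. At the only target the protocol states, it gives a false decline in more than half of no-change trials throughout the range examined. The exact percentages rest on the assumed model; the mismatch between a few inpatient tests and about 15 home tests does not.

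For medication adherence the gap is an unnamed measure and cut-off, not an invalid test. Inhaler misuse can be tested by McNemar as planned, once one of the two in-hospital assessments is named as the comparator. This should be corrected before analysis; no scheduled data are lost.

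**What to change.** Drop the pre/post McNemar test for device adherence and state instead:

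- **V-TTG:** the proportion with at least one session within 30 days of discharge, with exact 95% CI, over all participants discharged home, non-users counted as not adherent.
- **SpiroPD:** over the same denominator, the mean percentage of the 15 every-other-day tests completed, capped at 100% per person, with 95% CI, plus the proportion meeting the goal with exact 95% CI. Let the mean lead, because the goal is strict: under the assumptions above only 8-41% would complete all 15. State how readmission or death within 30 days changes the expected number of tests. METHODS OVERVIEW mentions reminders for daily monitoring and Data Collection Time Points a goal of every other day; these must be reconciled, and the 15 revised if the schedule differs.
- **Propeller:** a post-discharge estimate in the subset with 95% CI, and no pre/post comparison.
- **Medication adherence:** change in MARS, hospital against 30 days, preferably on the score by Wilcoxon signed-rank, or by McNemar with a cut-off fixed before the data are seen. Dose counters and the optional SpiroPD diary are descriptive.
- **Inhaler misuse:** keep McNemar, and name baseline or post-education (Data Collection Time Points, items 1 and 3) as the pre-discharge value.

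The cost is SAP wording, with no new data. Device adherence is then estimated without a p-value, and the pre/post medication-adherence claim under SA2 rests openly on self-report.
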